9.3 Schedule of Events

Schedule of Events		
Study Activity	Visit 1	Visit 2
Tetraphraph		X
Informed consent	X	
Review of Medical Record	X	
Adverse event evaluation		X

10 Statistical Plan

10.1 Sample Size Determination

Based on paired t test, 97 patients will provide 90% power to detect a difference of 0.5 min or larger between hands and feet at 0.05 significance level. A common standard deviation of 1.5 min for hands and feet is assumed based on previous work comparing flexor hallucis brevis and adductor pollicis muscles. However, we will enroll 130 patients to take into account patient loss or missing data. We want to determine a shorter time difference between hand and foot in order to make it applicable in all clinical settings, including rapid sequence induction and intubation.

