6.4 Primary Study Endpoints

The primary endpoint of the study will be time of onset of blockade and the rate of recovery following sugammadex administration as recorded simultaneously from the hand (adductor pollicis) and foot (flexor hallucis brevis) muscles.

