10.2 Statistical Methods

Descriptive Statistics

Analysis of agreement between the muscle groups will be compared between the two monitoring sites using the Wilcoxon signed rank test. The limits of agreement are defined as $\text{bias} \pm 2 \text{ SD}$, where SD denotes the standard deviations of the differences. Limits of agreement are interpreted as the reference range within which 95% of the differences will lie. The bias and the limits of agreements surrounding the bias ($\pm 2 \text{ SD}$) will be calculated with 95% confidence intervals. Statistical significance will be defined as a p-value <0.05 .

Handling of Missing Data

This is a prospective pilot study and therefore we do not anticipate any missing data. In the event of any unexpected missing data, no attempt to impute this missing data will be made;

missing data will simply be treated as missing in the statistical analysis, and replacement participants will be enrolled to achieve the target accrual of n=100 participants.

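### Is the 90% power at 97 patients undermined because 1.5 min is given as an SD for hands and feet rather than as the SD of the paired difference?

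*Combined protocol and SAP*

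**What the plan says.** Section 10.1 states: "Based on paired t test, 97 patients will provide 90% power to detect a difference of 0.5 min or larger between hands and feet", and sets the test "at 0.05 significance level" without saying whether it is one- or two-sided. The variability input is "A common standard deviation of 1.5 min for hands and feet is assumed based on previous work". The target is deliberately small: "We want to determine a shorter time difference between hand and foot in order to make it applicable in all clinical settings". Enrolment is set at 130, and the surplus over 97 is explained by patient loss or missing data.

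Section 6.4 confirms the pairing, since both responses are "recorded simultaneously from the hand (adductor pollicis) and foot (flexor hallucis brevis) muscles". Section 10.2 defines limits of agreement from bias and SD, "where SD denotes the standard deviations of the differences". It gives no planning value for that SD. No thumb-toe correlation appears anywhere in the document.

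**The concern.** An SD that is common to hands and feet describes two marginal distributions, one per site. A paired difference has a single SD, which equals the per-site SD only when the correlation is exactly 0.5. On the literal reading, the 90% rests on a correlation that nobody states.

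This is the plan's only power statement, and both the 97 and the 130 rest on it. If the correlation were well below 0.5, the study could miss the 0.5 min difference it was built to find. With 1.5 min per site and 97 patients, the difference detectable with 90% power runs from 0.71 min at correlation 0 to 0.39 min at correlation 0.7. The authors could have mislabelled the SD of the differences, assumed a correlation of 0.5 without saying so, or put a per-site SD into the wrong slot. The text does not tell these apart.

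**Working it through.** **Inputs.** From section 10.1: paired t test, n = 97, power 90%, difference 0.5 min, level 0.05, SD 1.5 min. Assumed, because the plan is silent: a two-sided test, and a range of correlations rho.

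**Method.** Exact paired t-test power from the noncentral t distribution, with n − 1 degrees of freedom and noncentrality 0.5 × √n / SD_diff.

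**Step 1: reproduce 97.** Take SD_diff = 1.5 min. The noncentrality at n = 97 is 0.5 × 9.849 / 1.5 = 3.28.

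- n = 96 gives 89.8% and n = 97 gives 90.1%, so 97 is the smallest sufficient number.
- The normal approximation gives (1.5 × (1.960 + 1.282) / 0.5)² = 94.6, that is 95. The plan's figure is the exact t result.
- A one-sided 0.05 test with the same SD would need only 79.
- Two independent groups with SD 1.5 min would need 190 per group, so the pairing was used.

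**Step 2: the literal reading.** With 1.5 min at each site, SD_diff = 1.5 × √(2(1 − rho)). At rho = 0.5 this is 1.5 × √1 = 1.5 min, so Step 1 and a per-site SD with rho = 0.5 are the same calculation. With a two-sided test, 97 is the minimum for 90% power only for SD_diff between 1.496 and 1.504 min (rho 0.497 to 0.503).

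**Step 3: sensitivity to rho.** Power is shown at 97 and at the other patient numbers the plan mentions: 100 in section 10.2, 120 in section 6.2 and 130 in section 10.1.

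| rho (assumed) | SD_diff, min | n = 97 | n = 100 | n = 120 | n = 130 | n for 90% |
|---|---|---|---|---|---|---|
| 0 | 2.12 | 63.2% | 64.6% | 72.6% | 76.0% | 192 |
| 0.3 | 1.77 | 78.4% | 79.7% | 86.5% | 89.0% | 135 |
| 0.4 | 1.64 | 84.3% | 85.4% | 91.1% | 93.1% | 116 |
| 0.5 | 1.50 | 90.1% | 91.0% | 95.2% | 96.5% | 97 |
| 0.6 | 1.34 | 95.3% | 95.8% | 98.2% | 98.8% | 78 |
| 0.7 | 1.16 | 98.7% | 98.9% | 99.7% | 99.8% | 59 |

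Power reaches 90% from rho of about 0.50 with 97 evaluable, 0.48 with 100, and 0.32 if all 130 are evaluable. The rho = 0 row is an extreme: both sites are measured at the same time in the same patient, under the same drug doses and anaesthetic.

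**Step 4: does the unlabelled input reach the results?** It does not. Section 10.2 takes the SD of the differences from the data and puts a 95% confidence interval on the bias. For n = 97 the half-width is about 1.985 × SD_diff / √97:

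- SD_diff = 1.5 min: 1.985 × 1.5 / 9.849 = 0.30 min.
- SD_diff = 2.12 min (rho = 0): 1.985 × 2.12 / 9.849 = 0.43 min.

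Even at the extreme, an interval centred on zero would exclude 0.5 min.

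**The case for a change.** The strongest case for a change is that the sentence says what it says. One SD shared by two sites is a per-site SD, and 97 is recovered only by reading it as something else or by adding a correlation. Nor is the surplus up to 130 a safe answer. Section 10.1 reserves it for loss and missing data, and section 10.2 names a target of 100, where power is 79.7% at rho 0.3. If 1.5 min really is per site and rho is 0.3 or lower, 90% power needs at least 135 patients, more than the plan enrols. A reader facing a null result would want to know which SD was meant.

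Much of this stands. The input is ambiguous, the calculations are correct, and it would be wrong to promise that no reading could ever call for more patients. It does not establish a fault in the design, however. The table runs both ways from rho = 0.5, and nothing in the document places the true value below that rather than above it. Only the earlier work on the two muscles could settle it, and its data are not in the document. A null result would be read from the observed interval, not from the planning SD.

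**Conclusion.** The concern does not call for a change. The figure of 97 is not an arithmetic error. It is the exact answer for a two-sided paired t test with an SD of differences of 1.5 min (90.1%), and a statistician checking it will arrive at that reading at once. What remains is a loosely labelled or unstated assumption. Naming it would leave enrolment, conduct, analysis and conclusions as they are.

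This rests on two assumptions: that the test is two-sided, which the match with 97 supports, and that the earlier work justifies 1.5 min for the difference, which the document does not let a reader verify. If 1.5 min is per site, power at 97 is 78% at rho 0.3, 84% at 0.4 and 95% at 0.6, so the true figure could lie on either side of 90%. Which endpoint the 0.5 min refers to, and the use of a signed rank test in section 10.2, are separate matters and are not judged here.

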10.2 Statistical Methods

Descriptive Statistics

Analysis of agreement between the muscle groups will be compared between the two monitoring sites using the Wilcoxon signed rank test. The limits of agreement are defined as $\text{bias} \pm 2 \text{ SD}$, where SD denotes the standard deviations of the differences. Limits of agreement are interpreted as the reference range within which 95% of the differences will lie. The bias and the limits of agreements surrounding the bias ($\pm 2 \text{ SD}$) will be calculated with 95% confidence intervals. Statistical significance will be defined as a p-value <0.05 .

Handling of Missing Data

This is a prospective pilot study and therefore we do not anticipate any missing data. In the event of any unexpected missing data, no attempt to impute this missing data will be made;

missing data will simply be treated as missing in the statistical analysis, and replacement participants will be enrolled to achieve the target accrual of n=100 participants.

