4.1 Abstract

Residual neuromuscular blockade is a common occurrence in the post-anesthesia care unit (PACU) when neuromuscular blocking agents (NMBAs) have been used in the operating room. The only method of reliably detecting residual neuromuscular blockade is through the use of quantitative neuromuscular monitors. Unfortunately, several barriers exist that have prevented the widespread use of these devices. For instance, there is a paucity of quantitative neuromuscular monitors commercially available. Also, two modalities of quantitative monitoring, kinemyography and acceleromyography, rely on movement of the muscles of interest, a characteristic frequently compromised during patient positioning for surgical procedures in which the patient's arms are secured under surgical drapes (laparoscopic, bariatric, robotic, spine, and neurosurgical procedures) or in uncooperative awake patients in the PACU or intensive care unit (ICU). The aim of this investigation is to determine the different muscle sensitivities to NMBA and reversal agents by comparing responses at two different monitoring sites as measured with a new quantitative monitor. The TetraGraph (Senzime AB, Uppsala, Sweden) is a standalone electromyography (EMG)-based quantitative monitor that recently received Conformité Européene (CE) and US Food and Drug Administration (FDA) approvals. EMG measures electrical activity within the muscle following peripheral nerve stimulation, and is unaffected by involuntary patient motion or by restricted muscle movements from surgical positioning. We plan to compare measurements obtained with two Tetraphraph devices, one monitoring the adductor pollicis (thumb) muscle and the other monitoring the flexor hallucis brevis (great toe) muscle, during onset, maintenance, and recovery of neuromuscular blockade. This will include monitoring every 20 sec for onset of blockade (defined as Train-of-four count, TOFC =0) following rocuronium administration, during maintenance of neuromuscular block as required by surgical conditions, and following reversal administration until adequate recovery is documented (train-of-four ratio, TOFR > 0.9).

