Utilizing recommendations from the Good Clinical Research Practice (GCRP) Guidelines for monitoring of neuromuscular function (Fuchs-Buder et al. 2007), we will investigate the performance of the TetraGraph at two muscle groups: adductor pollicis and flexor hallucis brevis. Specifically, the time points of interest will include the onset of blockade (Train-of-four count =0), maintenance of neuromuscular block as clinically indicated by surgical needs, and recovery from rocuronium blockade with sugammadex, and every 20 seconds following reversal administration until tracheal extubation (as determined by the SOC practice).

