9.2 Visit 2 (Randomization and Treatment – day of surgery)

- Elective surgical procedure as per standard of care
- Anesthetic management will include rocuronium, sevoflurane, and sugammadex at the discretion of the attending anesthesiologist as per standard of care practice.
- Prior to induction of anesthesia, Tetragraph electrodes will be placed over the ulnar nerve and the thumb to measure the response of adductor pollicis, and over the posterior tibial nerve and the great toe to measure the response of the flexor hallucis brevis.
- Following induction of anesthesia but prior to NMBA administration, baseline values will be recorded at both muscle groups after instrument calibration.
- Near the conclusion of the operation but prior to reversal of NMBA, another set of measurements will be taken at both muscle groups.
- Intraoperatively, measurements will be taken every minute until the sugammadex administration, as per usual clinical routine.
- After sugammadex administration, measurements will be taken every 20 seconds until the patient's trachea is extubated.
- Anesthesia providers will be guided on the intraoperative management of neuromuscular block based on the responses recorded from the adductor pollicis muscle, as per usual clinical routine.
- Each neurostimulation with the TetraGraph will be conducted simultaneously by a single study team member.
- Following measurements obtained with both devices at these specified time intervals and assuming TOF ratio is >0.9 , the devices will be disconnected and the patient will proceed along the standard recovery pathway.

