10.3 Subject Population(s) for Analysis

Each participant who goes through the surgery and completes monitoring of residual neuromuscular blockade will be included in the primary analysis regardless of study withdrawal for any reason. In the event of any study withdrawals, in secondary analysis we will examine the sensitivity of our results to the exclusion of patients who withdrew.

11 Safety and Adverse Events

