18.3 Monitoring data

Study ID				
Date of Surgery (dd / mm / yyyy):				
Initials:		Dominant side:	L / R	Age (yrs):
Wrist circumference (right):		Wrist circumference (left):		
Ankle circumference (right):		Ankle circumference (left):		
Weight (kg):		Height (cm):		BMI:

TetraGraph (TG)

Arm tested: dominant / non-dominant

	Thumb	Toe	TOFR #3 (if needed)
Calibrated baseline TOFR and supramax current			
Time to TOFC=0			
pre-SGX			
+20 sec			
+40 sec			
+60 sec			
+120 sec			
+140 sec			
+180 sec			
+200 sec			
+220 sec			
+240 sec			

+260 sec			
TOFC or TOFR +280 sec			
TOFC or TOFR +300 sec			
TOFC or TOFR at extubation			
Time to recovery following SGX (TOFR ≥ 0.9) (two consecutive measurements)			

19 List of In-Text Figures

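### The plan does not settle when study readings stop after sugammadex, and a site still unrecovered at its last reading falls under a missing-data rule that can bias the recovery comparison

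*Combined protocol and SAP*

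**What the plan says.** **When readings stop.** The abstract (4.1) runs readings "following reversal administration until adequate recovery is documented", meaning TOFR above 0.9, and names no site. Section 9.2 has a different end point: "After sugammadex administration, measurements will be taken every 20 seconds until the patient's trachea is extubated". Section 4.2 agrees with that and leaves the time of extubation to standard of care. The last bullet of 9.2 adds a condition for disconnecting the devices: "Following measurements obtained with both devices at these specified time intervals and assuming TOF ratio is >0.9". It does not say whether the ratio is the thumb's, the toe's or both, or what happens if it is not reached.

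**What counts as recovery.** Section 6.4 makes rate of recovery part of the primary endpoint without defining it. The only recovery time on the case report form is in Table 18.3: time to TOFR of at least 0.9 on two consecutive measurements. The form has no entry for a site that did not get there. The secondary endpoint (6.5), TOFR below 0.90 at extubation, shows that the plan foresees such cases.

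**What the analysis does.** Section 10.2 compares the sites with the Wilcoxon signed rank test and limits of agreement (bias ± 2 SD), both of which need a value from each site. On gaps it says that "missing data will simply be treated as missing in the statistical analysis, and replacement participants will be enrolled", up to a target of 100. Section 10.3 says: "Each participant who goes through the surgery and completes monitoring of residual neuromuscular blockade will be included in the primary analysis". Censoring is not mentioned anywhere.

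**The concern.** A toe that has not met the definition at its last reading is not an uninformative gap. Its recovery time is known to be longer than the time of that reading. Under 10.2 that information would be thrown away.

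The harm depends on what determines the stop. If it tends to follow thumb recovery, pairs with a fast toe are always complete and pairs with a slow toe are the ones lost. The retained toe-minus-thumb differences are then too low, the upper limit of agreement falls, and the Wilcoxon test can reject too often in the direction of a faster toe. Replacement patients pass through the same filter, so n is restored and the selection remains. Recovery is one of the two primary measures. Onset, the other, is complete before sugammadex is given and is not touched.

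**Working it through.** **1. The plan's own figure.** Section 10.1 gives 97 patients, 90% power, a difference of 0.5 min, SD 1.5 min and alpha 0.05. A two-sided paired t test (noncentral t) with SD of *differences* 1.5 min gives power 0.901 at n = 97, so the figure reproduces. If 1.5 min is instead each site's SD and the sites are uncorrelated, the SD of differences is 1.5 × √2 = 2.12 min and power at 97 is 63%. I use 1.5 min for the differences as the base case and vary it. Section 10.1 does not say whether it refers to onset or recovery, and its mention of rapid sequence induction points to onset.

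**2. Model (assumed).** Let D = toe recovery time minus thumb recovery time, normal with mean μ and SD σ. Let g be the time for which readings continue after thumb recovery. A pair is complete only if D ≤ g. With a = (g − μ)/σ and λ = φ(a)/Φ(a):

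- share lost = 1 − Φ(a)
- retained mean = μ − σλ
- retained SD = σ√(1 − aλ − λ²)

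Neither g nor μ is in the documents.

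**3. Results for μ = 0.5, σ = 1.5.**

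| g (min) | a | φ(a) | Φ(a) | lost | retained mean |
|---|---|---|---|---|---|
| 1 | 0.333 | 0.3774 | 0.6306 | 37% | 0.5 − 1.5 × 0.5985 = −0.40 |
| 2 | 1.000 | 0.2420 | 0.8413 | 16% | 0.5 − 1.5 × 0.2876 = +0.07 |
| 3 | 1.667 | 0.0995 | 0.9522 | 5% | 0.5 − 1.5 × 0.1045 = +0.34 |
| 5 | 3.000 | 0.0044 | 0.9987 | 0.1% | +0.49 |

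At g = 2 the retained SD is 1.5 × √(1 − 0.2876 − 0.0827) = 1.19. The limits become 0.07 ± 2.38, or −2.31 to 2.45, against true limits of 0.5 ± 3.0, or −2.50 to 3.50.

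**4. Other SDs, μ = 0.5.** Retained means at g = 1 / 2 / 3 min are:

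- SD 1.0: −0.01 / +0.36 / +0.48
- SD 0.75: +0.18 / +0.46 / +0.50
- SD 2.12: −0.89 / −0.37 / +0.02, and +0.41 at 5 min

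**5. Wilcoxon at true lag 0.** With SD 1.5 and 100 complete pairs after replacement, simulated rejection is about 100%, 37% and 8% for g = 1, 2 and 3 min, nearly all of the excess saying the toe is faster. With 130 enrolled and no replacement, repeated runs give about 100%, 41 to 44% and 7%. With 130 enrolled and SD 1.0 the figures are 89%, 9% and 4%; with SD 0.75 they are 44%, 6% and 6%. With SD 1.5 and a true lag of 0.5 min, power at n = 100 is 0.89 for g = 5, 0.75 for g = 3 and 0.18 for g = 2.

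**6. Stops not tied to the thumb.** With a stop time independent of both sites (normal, centred 2 min after the mean thumb time, SD 1.5), 29% of pairs are lost, the mean at true lag 0.5 is +0.42, and the Wilcoxon keeps its 5% level at lag 0. Skewed recovery times cut off at a fixed 300 s for both sites behave the same way: no bias at lag 0, and 0.50 shrinks to 0.42. If both sites are read to recovery, no pair is lost.

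**The case against.** The strongest reply is that the stop texts can be read as one rule. The abstract describes two devices. The last bullet of 9.2 refers to measurements with both of them and disconnects them together, assuming TOFR above 0.9. Read as both sites recovered, almost nothing is lost. That reading is fair, but it is not stated, and 4.2 and another bullet of 9.2 stop at extubation with no recovery condition.

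Four stronger readings are tempting and are not supported.

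- *A reader might infer that 10.3 also excludes the patient.* It does not. A patient read until extubation has completed monitoring as 9.2 describes it. Only 10.2 leads to loss of the pair, and only if recovery is analysed as the Table 18.3 time. A slope, or TOFR at fixed times, could use incomplete recoveries, though no such analysis is specified.
- *A reader might infer that extubation follows thumb recovery.* Section 9.2 says "Anesthesia providers will be guided on the intraoperative management of neuromuscular block based on the responses recorded from the adductor pollicis muscle". That covers intraoperative management. Section 4.2 leaves extubation to standard of care, and Table 18.2 allows other monitors and sites at extubation. Section 11.1.4 mentions TOFR after arrival in the recovery unit, but as an adverse-event window and not as a study reading.
- *A reader might infer that the plan will produce a false finding of a faster toe.* The large figures need an SD near 1.5 min and a stop within about 2 min of thumb recovery. The documents give neither for recovery.
- *A reader might infer that the Wilcoxon should give way to a sign test as the main recovery test.* The sign test asks which site recovers first, which is not the 0.5 min difference the study is powered on. Its power is 84%, against about 96% for an uncensored Wilcoxon (n = 130, lag 0.5, SD 1.5).

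**Conclusion.** The point stands in conditional form. The stop wording is inconsistent, and the only rule that reaches an unrecovered site treats a partly known time as missing and replaces the patient. That can bias one of the two primary measures, so it is more than an omitted detail.

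The direction toward a faster toe rests on four assumptions: readings end at extubation, that is soon after thumb recovery, some toes lag beyond it, and recovery is analysed as the Table 18.3 time. With SD of differences 1.5 min and a true lag of 0.5 min, the shift is −0.90, −0.43 and −0.16 min for stops at 1, 2 and 3 min. It is small at 3 min or more with that SD, and at 2 min or more with the smaller SDs tried. It would last longer only with an SD above the one that reproduces the plan's n. A stop unrelated to the thumb mainly shrinks a real difference. Confidence is medium, because the documents do not say which case applies.

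**What to change.** 1. **Stop rule.** Reconcile 4.1, 4.2 and 9.2 on when study readings stop and at which site. This concerns study readings only and asks for no change to extubation practice. If both-site recovery is what is meant, one sentence saying so removes most of the problem.
2. **Section 10.2.** State that a site not meeting the Table 18.3 definition at its last reading is censored at that time, not missing, and that the patient is kept and not replaced.
3. **Reporting.** Give the number censored per site, including unrecovered thumbs. If any are censored:
   - report the median difference, with pairs where only the toe is unrecovered ranked as longest;
   - take bias and limits of agreement from a censored-data estimate;
   - give the within-patient sign test (which site recovered first) and the complete-case Wilcoxon as sensitivity analyses.

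The onset analysis stays as it is.

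**Cost.** This is wording and modest analysis work. No new data are needed: serial readings are on the form, and 8.1 says that all intraoperative data are downloaded from the device.

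**Downsides.** The censored limits need a distributional assumption. In simulation under a matching normal model (SD 1.5), the estimate at true lag 0.5 was 0.52 and 0.50 for stops at 1 and 2 min. The median was 0.50 for stops at 1 to 3 min, but could not be estimated in 86% of trials with a stop at 20 s. The sign test has lower power. It also gives no protection if readings stop before thumb recovery: with 20% of patients stopped 20 s before it, the test rejects 15% of the time at lag 0, and 7% if 10% are. That is why the stop rule should be settled first.

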6.1 General Description

[figure not shown]
This pilot unblinded, single center, prospective, randomized, observational study will involve 130 patients undergoing surgical procedure that requires administration of neuromuscular blocking agents intraoperatively.

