6.2 Number of Subjects

One hundred twenty

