12.7 Data Quality Assurance

Once the study is completed the Principal Investigator will randomly select 3 participants and compare the data documented in the EHR with what is entered into the REDCap database. If there is any discrepancy, the Principal Investigator and/or Investigators will cross-reference all 100 patients to ensure accuracy.

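### The planned sample size is 130, 120 or 100 depending on the section, so the number that ends enrolment is not uniquely defined

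*Combined protocol and SAP*

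**What the plan says.** Three totals stand in the current text.

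- **130.** The Study Summary lists 130 subjects. Section 6.1 says the "observational study will involve 130 patients undergoing surgical procedure". Section 10.1 ties the figure to the power calculation: "97 patients will provide 90% power to detect a difference of 0.5 min or larger", followed by "However, we will enroll 130 patients to take into account patient loss or missing data".
- **120.** Section 6.2, the section headed Number of Subjects, reads in full "One hundred twenty".
- **100.** Section 10.2, under Handling of Missing Data, says "replacement participants will be enrolled to achieve the target accrual of n=100 participants". Section 12.7 says that, if a data check finds a discrepancy, the investigators will "cross-reference all 100 patients to ensure accuracy".

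On missing data, Section 10.2 states "This is a prospective pilot study and therefore we do not anticipate any missing data". Section 10.1 adds patients for exactly that reason but gives no loss rate. Section 7.3 says accrual time will be extended after the first 3 months as needed to reach a target, and does not say which number that is.

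**The concern.** The number enrolled should be fixed in advance and readable from any section that states it. Here Sections 6.1 and 6.2 disagree although they are consecutive, and the statistical section contradicts itself between 10.1 and 10.2.

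The 100 is also unlabelled. Speaking of accrual suggests patients enrolled. Replacing patients because data are missing suggests patients with complete data. Section 12.7 uses 100 as if it were the whole cohort. Section 10.3 defines who enters the primary analysis, but it does not link that population to 100 or to any other number.

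At stake is when recruitment stops. Section 7.3 aims for at least 10 participants a week and takes stock after at least 3 months. At exactly 10 a week, 100 is reached in week 10, 120 in week 12 and 130 in week 13. The three totals therefore separate at about the time the plan says further accrual will be decided. The study is open-label, so it is better that nobody has to choose among them at that point.

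**Working it through.** **Inputs from Section 10.1.** Paired t test; difference 0.5 min; SD 1.5 min; significance level 0.05; power 90%. Two choices are mine: a two-sided test, and reading 1.5 min as the SD of the paired differences. The text says "A common standard deviation of 1.5 min for hands and feet is assumed", which does not settle the second choice, but this reading returns the plan's figure.

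**Reproducing 97.** The normal approximation gives n = [1.5 × (1.960 + 1.282) / 0.5]² = 94.6, so 95. The exact calculation uses the noncentral t distribution with n − 1 degrees of freedom and noncentrality (0.5/1.5)√n. It gives power of 89.85% at 96 and 90.15% at 97, so 97 is the smallest adequate number and the plan's figure is confirmed.

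**The three totals against 97.** The third column is (N − 97)/N, the loss each total could absorb if it were the number enrolled and still leave 97.

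| Total N | Power if all N are evaluable (paired t) | Loss leaving 97 |
|---|---|---|
| 100 | 91.0% | 3/100 = 3.0% |
| 120 | 95.2% | 23/120 = 19.2% |
| 130 | 96.5% | 33/130 = 25.4% |

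No stated loss rate leads from 97 to any of these totals. The 25.4% is what 130 implies, not a figure the plan gives.

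**Can the totals be reconciled?** 130 and 100 can coexist: 100 complete patients out of 130 enrolled is a loss of 30/130 = 23.1%. The plan does not say that this is meant. 120 against 130 cannot be reconciled this way, because neither 6.1 nor 6.2 distinguishes enrolled from evaluable patients. In 12.7, 100 conflicts with 130 if it means everyone enrolled.

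**The named test.** Section 10.2 compares the two sites with the Wilcoxon signed rank test, not the paired t test used for sizing. In a simulation with normal differences (mean 0.5, SD 1.5, two-sided 0.05, 200,000 runs), Wilcoxon power was 88.8% at 97, 89.7% at 100, 90.2% at 102 and 95.7% at 130. Normality is an assumption. This matters only if a minimum of 97 or 100 evaluable patients is written into the plan.

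**The case against.** The strongest reply is that nothing is lost in practice. The 97 is correct, every stated total is above it, and 10.2 provides for replacements, which most naturally means about 100 complete patients within the 130. On that view the three numbers are leftovers of editing. Most of this stands, and it limits the point to consistency. It does not explain the 120, and it does not tell a reader which number ends recruitment.

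Two stronger readings are tempting, and the documents do not support either.

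- A reader might infer that the study could fall below 90% power, taking 100 as a cap on enrolment with losses on top. The sentence that gives the 100 says replacements will be enrolled to reach it, so that scenario is not the plan as written.
- A reader might infer inflated type I error from the interim analysis mentioned in 7.3. That section links the look to extending accrual time and states no test of thumb against toe and no stopping rule. A review of accrual is a plausible reading.

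**Conclusion.** The inconsistency is real and should be corrected. Enrolment could end at 100, 120 or 130, a spread of 30 patients, and the two statements on missing data in 10.1 and 10.2 conflict. There is no arithmetic error and no demonstrated loss of power: the 97 reproduces, and power with all patients evaluable runs from 91.0% at 100 to 96.5% at 130. These figures rest on the paired t test, two-sided, with 1.5 min as the SD of the differences. Under the Wilcoxon test and normal differences, 100 evaluable gives just about 90% and 130 about 96%. The facts about the totals depend on none of these assumptions.

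**What to change.** Use 130 enrolled as the single stopping number, as 10.1 already states.

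- **6.2:** change the number to 130.
- **7.3:** say that the accrual target is 130 enrolled.
- **10.1:** state the sponsor's own assumed loss rate. For reference, 130 against 97 implies about 25%.
- **10.2:** delete the statement "This is a prospective pilot study and therefore we do not anticipate any missing data". Then either remove the replacement rule with its 100, or relabel 100 as the minimum number of evaluable patients expected within the 130, with enrolment continuing to 130 in either case. If the minimum stays, define evaluable as the Section 10.3 population with a usable paired thumb and toe value for the primary endpoint. Note also that Wilcoxon power is about 89% at 97 and about 90% at 100, assuming normal differences.
- **12.7:** refer to all enrolled patients instead of 100.

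The cost is wording in five sections. No patients are added beyond the 130 already planned, and no procedure changes.
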